Table 2. Assessment schedule

Principal Investigator: [name]

Protocol Summary for IRB: Feasibility Study of Couple Therapy Treatment for Situational Couple Violence (IRB# 09-13-27)

Efficacy & Data Analysis

Data analysis plan

This study is designed to be an initial feasibility study to collect pilot data in pursuit of the following aims:

Aim 1: After the first wave of data collection (pretest), the cross sectional relations among the basic constructs of interest will be examined. These basic constructs are psychophysiological markers of emotion regulation and IPV. In order to understand how these markers are related to violence, t-tests will be used to understand this effect. Each partner's HPA and PNS activity is expected to be directly linked to the violence perpetrated by their partner.

Aim 2: The objective of this aim is to understand whether violence decreases over time following therapy and whether this decrease is accompanied by respective change in physiological markers of emotion regulation. For this purpose, series of chi-square-test will be used as well as qualitative analysis.

Aim 3: In order to represent the interaction between the emotion regulation of partners, links from emotion regulation of each partner to the emotion regulation of the other partner at the next time point are included. Qualitative analysis with a grounded theory approach will be used.

The proposed sample size (8 couples) is chosen as a tradeoff between data collection time and statistical power. Since this is a feasibility study, we chose to start with a small sample size. GPower was used to estimate statistical power for the primary hypotheses. Assuming 8 couples (16 participants), with 4 couples in each group and two waves of data each, the statistical significance can be detected. Specifically, with power = .40, this study can detect an effect size of $f = .80$ (Using t-test statistics). Also chi-square test will be used to test the effectiveness of the intervention with power = .40. With this level of power, this study can detect an effect size of $f = .60$ (Using chi-square statistics).

The PI will continually monitor the study design to determine if there is a need to make modifications or discontinue the study due to lack of efficacy from therapeutic intervention.

Safety

Compensation for research related injury

In the event that a participant sustains physical injury as a result of participation in this investigation, all necessary and appropriate care will be provided. However, UH may not pay for the costs of treatment for injuries that result from noncompliance with study procedures.

Safety Information

There are a number of interventions cited in the literature for clinicians concerned about violence occurring between partners in between therapy sessions. The below violence prevention strategies and safety interventions from the literature will be used in this project to deal with situations that may arise. In the following, the general strategy is highlighted in *italics*, followed by a description of how the strategy will be applied in this study.

Principal Investigator: [name]

Protocol Summary for IRB: Feasibility Study of Couple Therapy Treatment for Situational Couple Violence (IRB# 09-13-27)

1. *Identify the conflict issues between the couple and discuss situations in which violence may be prompted along with what can be done to avoid or work against such situations.* This violence prevention strategy will be widely discussed during the couple therapy sessions as part of the proposed intervention. Please see the treatment manual.
2. *Identify the risk factors for further violence, including substance abuse, severe mental health problems, having previously violent relationships, access to firearms, and comfort with severe violence.* Participants with high risk of severe intimate partner violence will be identified and these participants will be excluded from the study. Please see details about the exclusion criteria.
3. *Identify the techniques that participants can use at home when they feel that a situation may be escalating out of control and teach these techniques to the participants.* The following techniques will be taught the participants in this study:
 - a) Timeout procedures: The participants will be taught of ways of identifying a situation that is getting hostile by recognizing cues that lead to high conflict and walking away when they identify such a situation.
 - b) Stress management techniques: Participants will be taught of breathing exercises, guided imagery, and safe place techniques to deal with stressful situations. Handouts will be provided (Please see appendix for the handouts).
 - c) Anger control and problem solving techniques will be taught as part of the couple therapy.
4. *Specify safety planning for worst case scenarios.* Participants will be taught of safety planning and handouts will be provided (Please see appendix for the handouts).
5. *Provide a referral sheet for the participants with numbers and locations of various emergency services as well as 24 hour hotline numbers.* A referral sheet will be provided to the participants. The referral sheet will also include numbers and locations of area mental health providers as well as the fee associated with their services. (Please see appendix for the referral sheet).
6. *Monitor possible buildup tension between the partners.* The therapists will see the participants in weekly scheduled sessions and will call the participants at least once in between sessions to monitor the buildup of tension.
7. *Meet each partner individually for safety assessment.* The therapists will meet clients individually after each session to make sure that they feel safe going home with their partners. If not, the therapist will encourage the two to separate to avoid any violent situations. Each partner will also be provided by a phone number at which they can reach the therapist and arrange for individual time with the therapist if they wish to.
8. *Provide an emergency contact number for the participants.* The participants will be provided a phone number of an experienced therapist to contact in case of emergencies. This phone number will be associated with a voice mail that is remotely accessible. Participants will also be advised to call 911 in case of emergencies that needs prompt response.

Risk Management

Plans for subjects at the end of the protocol:

After completion of the project and follow-up data collection, participants will be briefed about the study and some preliminary findings will be shared. Participants will also be provided with

Principal Investigator: [name]

Protocol Summary for IRB: Feasibility Study of Couple Therapy Treatment for Situational Couple Violence (IRB# 09-13-27)

referral information in case of future need. After data is analyzed and the results are published, the data will be destroyed.

The therapy that participants are receiving is not experimental, rather the data collection procedures comprise the research. After 8 weeks of sessions, if participants request additional therapy, the PI will continue to be their therapist until their issue is resolved or they secure another therapist. The PI will also provide referral information in case participants would like to continue with another therapist.

Data and Safety Monitoring

Data Monitoring. The proposed research will include data from approximately 8 couples. The final dataset will include self-reported demographic and behavioral data, along with cortisol levels and heart rate information. All identifiers will be removed from the final dataset prior to release for sharing.

Data will be reviewed after every assessment session. The PI will analyze the data from the first cohort before proceeding with the next to determine if the research should proceed as planned, if PI needs to modify the protocol or discontinue the research (e.g., if Group 2 is doing better than Group 1).

Safety Monitoring. The PI will be responsible for monitoring the safety of the participants. In this study, the welfare of the participants will be of primary concern during treatment. There are a number of interventions cited in the literature for clinicians concerned about violence occurring between partners in between therapy sessions. Several prevention strategies and safety interventions from the literature will be used to prevent and deal with situations that may arise. These strategies and interventions are described in the attached Safety Chart.

Careful assessment will be conducted to understand the dynamics of situational couple violence and potential safety issues that couples are experiencing. The PI will ask questions about whether participants feel they are in danger. If participants are afraid that their partner will retaliate after disclosing sensitive information, these couples will be excluded from the study. Withdrawal from the study will be honored without any coercion.

Treatment will not begin until both partners have been informed about the possible disruption and emotional upheaval that might arise during the 8 therapeutic sessions. As a safeguard, all participants will be taught stress and anger management strategies, such as: calm place, the light stream technique, spiral technique, breathing shift, and diaphragmatic breathing. (Please see attached information about these techniques). These techniques are frequently used in eye movement desensitization and reprocessing (EMDR) therapies as one of the evidence based treatments for Post-Traumatic Stress Disorder (PTSD), including treatment of veterans by the Department of Defense (American Psychiatric Association, 2004). A referral information sheet will also be provided to each participant. The same clinical precautions/procedures will be used if a participant expresses self harm.

Principal Investigator: [name]

Protocol Summary for IRB: Feasibility Study of Couple Therapy Treatment for Situational Couple Violence (IRB# 09-13-27)

Prior to leaving the therapy session, participants will be asked about their anger level. If they report being angry, they will be asked to remain at the research site until they have calmed down. Participants will also be asked about how safe they are feeling before leaving the session. For fearful participants, safety planning will be offered along with referrals and shelter information. The PI will call the local police at any time if a participant becomes aggressive or s/he feels threatened. In their 10 years of experience conducting the couple's treatment program with violent couples, McCollum and Stith (2008) reported that no involvement of local police was needed.

In order to help those in the control group who will not be receiving therapy for the first 8 weeks, individuals in this group will be taught safety planning, given information on local resources to help victims of violence, and will be instructed on stress and anger management strategies.

Subject Privacy

Consents will be received after the prescreening interview. For any interaction with the participants and the PI, the setting will be a private and secure room at the UH Mood Disorders Program. The room will be equipped with noisemakers to make the conversations private and not understandable by outside listening.

Data Sample Confidentiality

Participation in the study is confidential. Only the PI will know the participants' identity. Data will be de-identified. Traditionally used identifying information about participants, such as name, address, telephone number, or social security number, will not be put into either the public or controlled access databases for this project. Participants will have individual personalized login numbers to ensure that assessments at each data collection time connect to the correct participant. Participants will be contacted via email and telephone to remind them of the 3-month follow up assessment. None of the data will be entered into the participants' medical records and no study information will be shared with participants' physicians.

Confidentiality of the data will be maintained within legal limits. Access to participants' records will be limited to the PI. However, the study records must be available for review. The institutional Review Board (IRB) at University Hospitals of Cleveland, and other regulatory agencies may need to review study records.

The PI will receive a Certificate of Confidentiality from the government. This certificate protects against the involuntary release of information about participants collected during the course of this research. Since IRB approval is required to apply for a Certificate of Confidentiality, the PI will apply for the Certificate of Confidentiality after IRB approval is obtained. Nobody will be enrolled in the study before Certificate of Confidentiality is obtained.

The PI has been trained and certified in human subjects research. Information will be disclosed only with the participant's permission or as required by U.S. or Ohio law. Research personnel involved in this study cannot be forced to disclose any information collected in this study in legal proceedings. However, the PI is not prevented from taking the necessary steps, including reporting to authorities, to prevent serious harm to the subject or others, specifically children. In

Principal Investigator: [name]

Protocol Summary for IRB: Feasibility Study of Couple Therapy Treatment for Situational Couple Violence (IRB# 09-13-27)

this case, an appropriate Department of Children Services in the participant's community will be notified if anyone on the research team suspects a child is experiencing abuse.

All data and participant contact information will be destroyed at the end of the study period, following publication. If any results of the research are published, no information that could identify the participants will be released.

Data/Sample Security

Data collection and data security will be performed using RedCap. Paper versions for the technical problems will be entered to the redcap system as soon as technical problems were solved. These paper versions will be de-identified and will not include any identifying information. Data collected via RedCap will be password-protected. Participant assessment data will be confidentially downloaded into the CWRU secure computer server. Staff at the Office of Information and Technology at UH and CWRU will ensure downloaded data continues to remain secure, and they will create computer password links so that only the PI can have access to participant data. De-identified data located on the secure UH computer server will be translated into a readable Excel database at the completion of all study assessments. The data will be stored on the Case Western Reserve University network. Data transfers between computers will be protected by SSL encryption. If researchers need to transfer data outside of the network, an ironpad will be used to ensure security of the data.

The status of all participant data will be monitored by the PI on a weekly basis (e.g., assessments completed, drop outs). The data downloaded to Excel will be kept in a password protected program folder on a password protected local hard drive that will be physically located in a locked environment. Although the computer is a part of Case/UHCMC network, the database will not be accessible via the Case/UHCMC network. Only the PI will have the access to the data.

We recognize the sensitive nature of our research and the need to maintain strict confidentiality. We will take the following necessary steps to do so:

1. No record of participation in the study will be entered into the medical records of the participant.
2. We will implement the following schema for managing the linking of the data:
 - a) Prior to participant enrollment, we will generate sets of unique barcode labels, referred to as the ID.
 - b) Informed consent will be obtained and the participant will be enrolled in the study.
 - c) Study staff will use one set of barcodes for each participant, placing bar a code on each data sample. The unused labels will be retained in a study folder until the end of the study and then destroyed.
 - d) The code linking the ID with the participant's information will be kept in a password protected database separate from the primary database.

Principal Investigator: [name]

Protocol Summary for IRB: Feasibility Study of Couple Therapy Treatment for Situational Couple Violence (IRB# 09-13-27)

Financial Considerations

Payments to Subjects

Participants will receive \$20 (\$40 per couple) for each assessment session. In order to receive this amount, individuals must participate as a couple. The study has three assessment sessions. Participants will be paid for their initial visit and then \$20 for all three assessment sessions. Participants who complete the study will receive a total of \$80 (\$160 per couple). Additionally, the participants will be provided \$5 dollars per couple to cover the parking expenses, totaling \$60.

Due to their longer involvement in the study and one additional assessment sessions, participants in the Group 2 will receive additional monetary compensation. Group 2 participants who complete the study will receive a total of \$100 (\$200 per couple). Group 2 participants will also receive \$5 parking reimbursement, totaling \$65.

Costs to Subjects

Costs to the participant include transportation to the research site. Participants will be reimbursed for parking, but they will not be reimbursed for gas or public transportation.

Risks and Benefits

Risks

There is a chance that some participants, either due to the intervention or due to completing the questionnaires, will be encouraged to think about aspects of themselves or their relationships that they had not considered previously. If so, these thoughts could be stressful and upsetting.

Participants may become distressed due to the sensitivity of the particular topic. There is also a risk of unanticipated change in the participants' relationship. One of the risks of couple's therapy is the end of the relationship or divorce as a possible outcome of the partners gaining insight into the relationship. In clinical trials, attachment based therapies have been shown to be effective in treating couples with negative affect cycles and conflicts (Johnson & Whiffen, 1999), however, there may be a risk of escalation of conflict during the study. Several prevention strategies and safety interventions from the literature will be used to prevent and deal with such situations. Please see Section 16.1 (Data and Safety Monitoring for a detailed plan for maintaining the safety of the participants).

Benefits

The participants may benefit from this study in terms of improved handling of conflict in their relationship.

Alternatives to participation

Alternative treatment options are available in the community to treat IPV. These options include anger management groups for the offenders and self-esteem groups for the survivors of IPV. Also, participants can seek individual and couple therapy as alternative treatment options. Participants will be provided with a list of alternative treatment options during the informed consent procedure so as to avoid undue influence or coercion. Please see the appendices for the list of care providers and local resources.

Principal Investigator: [name]

Protocol Summary for IRB: Feasibility Study of Couple Therapy Treatment for Situational Couple Violence (IRB# 09-13-27)

Withdrawal from Study Participation

Voluntary participation. Participation is completely voluntary, and participants will be encouraged to terminate their participation in the proposed study if they express discomfort. If the couple chooses to withdraw from the study, they will be referred to other therapy and the referral list will be provided.

Both partners need to be willing to attend the therapy. If one partner decides to quit the study, we will stop and referrals will be provided. If one or more of the participants are willing to continue therapy individually, the PI will continue to see them individually until each of them secures a therapist. In that case, data collection with the couple will be discontinued.

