The purpose of this study is to understand whether the couple therapy that is used in practice is effective in preventing situational couple violence. More specifically, we will focus on couples with mild to moderate forms of situational couple violence to investigate how couple therapy can be effective in preventing the escalation and recurrence of situational couple violence. For this purpose, the response of partners to therapy will be investigated by integrating self-report questionnaires and psycho-physiological markers of emotion. All couples who exhibit characteristics of characterological violence will be excluded from the study.

The change in partners' emotion regulation over the course of therapy will be measured using psycho-physiological markers of stress response. Using these measurements, the interplay between changes in violence and the emotion regulation of partners in relation to each other will be investigated in a dyadic (couple) context. More specifically, the following aims will be pursued to understand the relationship between couple therapy, emotion regulation, and violence:

Aim 1: Examine the associations between IPV and each partner's psychophysiological regulation in terms of Hypothalamic Pituitary Adrenal (HPA) activity and Parasympathetic Nervous System (PNS) activity. This aim will investigate whether dysregulation of HPA and PNS activity in each partner is correlated with the existence and intensity of IPV for the couple. Existence and intensity of IPV will be assessed using self and partner report questionnaires. HPA activity will be measured using salivary cortisol, and PNS activity will be measured using vagal tone and vagal regulation by using an eMotion Heart Rate Variability (HRV) sensor.

Aim 2: Examine the longitudinal effects of conjoint therapy on IPV and each partner's psychophysiological regulation in terms of HPA and PNS activity. This aim will investigate whether the reported intensity of IPV for couples decreases after couples start therapy and whether this change is correlated with regulation of HPA and PNS activity for each partner. This aim will examine the effect of couple therapy on each individual partner separately.

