Aim 3: Examine the longitudinal effects of partners' psychophysiological regulation on each other's psychophysiological regulation and on IPV. This aim will explore patterns of change in each partner's psychophysiological regulation as a function of their partner's psychophysiological regulation. More specifically, this aim will investigate whether couple therapy facilitates change by restructuring the relationship in such a way that the change in one partner's behavior helps the other partner regulate their emotions in a functional way.

Principal Investigator: [name]

Protocol Summary for IRB: Feasibility Study of Couple Therapy Treatment for Situational Couple Violence (IRB# 09-13-27)

Study Design

This study has a longitudinal design that requires therapy sessions over 8 weeks, with data collected at every visit. Couple therapy will be conducted using an attachment and affect regulation based therapy approach described below under “Couple Therapy”. Data will be collected in the form of self-report and partner-report measures, as well as physiological screening of the neuroendocrine system. These measures are described below under “Data Collection”. The flowchart for the design of the study is shown below.

After careful screening, eight couples will be enrolled in the study. The couples will be divided into two groups, each consisting of four couples. Distribution of participants to the two groups will be randomized. Group 1 will immediately begin 8 weeks of couple therapy and Group 2 will complete 8 weeks of couple therapy after an 8 week (+ or – 10 days) waiting period is completed.

The pre-test, post-test, and follow-up physiological data collection will be completed at the following times for couples beginning the 8 weeks of couple therapy:

- Baseline Pre-test: Before starting the therapy sessions.
- Post-test: One week (+ or – 5 days) after the end of the therapy session.
- Follow-up: Three months (+ or – 10 days) after the post-test.

The participants that are assigned to Group 2 will also complete the physiological data collection before starting the 8 week waiting period. When participating in the 8 week couple therapy Group, participants will complete a small number of assessments at each therapy session.

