The main hypothesis of the proposed study is that conjoint therapy will gradually promote affect regulation of both partners in orchestration; i.e., improvement in one partners' ability to regulate emotions will have a positive effect in the other partner's ability to regulate emotions. If the outcome of this project supports this hypothesis, these results will provide biologically interpretable and quantitative grounds for the effectiveness of conjoint therapy and pave the way for more comprehensive and large scale effectiveness studies, which, in turn, may establish conjoint therapy as a strategy that will complement "parallel track" treatment in preventing and diminishing IPV.

The physiological processes that were found to link attachment and affect regulation include parasympathetic regulation of heart rate and Hypothalamic Pituitary Adrenal (HPA) axis activity (Beauchaine, 2001; Böhnke, Bertsch, Kruk, & Naumann, 2010; Porges, 2001). There is increasing evidence for the role of HPA axis in the development and enhancement of aggressive behavior in youth as well as adults. Furthermore, cardiac vagal tone, a common physiological marker of the regulation of the Parasympathetic Nervous System (PNS), is correlated with both anxious and disruptive behaviors (Böhnke, Bertsch, Kruk, & Naumann, 2010; Porges, 2001). Putting these observations together, the proposed research further hypothesizes that, through promotion of affect regulation, attachment based couple therapy will enhance regulation of PNS and HPA activity in couples, which in turn will have a diminishing effect on IPV.

In summary, the proposed research integrates research findings on the links between couple therapy, affect regulation, physiological markers of emotion regulation, and IPV to hypothesize and test a novel psychophysiological model for the mechanisms of change induced by couple therapy in the context of IPV.

Target Subject Population

Subject population:

Inclusion criteria:

- 1) This study is open to married, dating, and cohabiting couples.
- 2) Couples will have to be involved in an intimate relationship for at least one year with the current partner.
- 3) Both partners have to be older than 18 years of age at the time they signed the consent form.
- 4) Couples must have mild to moderate forms of situational couple violence.

Principal Investigator: [name]

Protocol Summary for IRB: Feasibility Study of Couple Therapy Treatment for Situational Couple Violence (IRB# 09-13-27)

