All participants in therapy appear more flexible in their relationship positions to one another. Responses are empathetic and emotionally receptive. Both partners monitor and regulate negative affect in an emotionally engaged manner. A sense of connectedness exists between both partners, as well as a decrease in negative cycles.

Principal Investigator: [name]

Protocol Summary for IRB: Feasibility Study of Couple Therapy Treatment for Situational Couple Violence (IRB# 09-13-27)

Data Collection

For each couple, data will be collected at each visit. Data will be collected in two forms:

1. Self-report and partner-report questionnaires will be collected using several measures, all of which have adequate reliability and validity.
2. Physiological data will be collected by monitoring heart rate variability and cortisol level at the DCRU.

Screening Measures

In order to examine eligibility, demographics and some clinical data will be collected.

- CAGE questionnaire. CAGE is a brief alcoholism screening test (Mayfield D, McLeod G, Hall P.1974)
- Simple Screening Instrument for Substance (SSI-SA). Abuse (SSI-SA) The SSI-SA was intended as a brief screen of substance abuse symptoms. It was designed utilizing a binary (yes/no) response format to facilitate scoring and to minimize subjective interpretation of scores Center for Substance Abuse Treatment. (1994).
- Conflict Tactics Scale 2 (CTS2;Straus, Hamby, BoneyMcCoy, & Sugarman, 1996) assesses intimate partner violence based on partners' rating of their own and their spouse's conflict strategies, measuring the intensity and frequency of psychological/verbal and physical conflict. This scale has been shown to have good reliability and validity (Straus, Hamby, BoneyMcCoy, & Sugarman, 1996). This is also be used throughout the study to monitor couple's relationship change.
- Symptom Checklist (SCL90-R) (Derogatis, 1994) will be used to assess acute psychopathology. This measure will also be used throughout the study to monitor participants' mental health change.

Outcome Measures

Both behavioral and physiological measurements will be used to evaluate the effectiveness of conjoint therapy. No medical records will be reviewed at any time.

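### Aim 1 asks how physiology correlates with partner violence, but the plan names only t-tests and defines no groups by violence; correlations with the CTS2 score should replace them

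*Combined protocol and SAP*

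**What the plan says.** The section Purpose states Aim 1 as an association: whether "dysregulation of HPA and PNS activity in each partner is correlated with the existence and intensity of IPV for the couple". IPV is to be assessed by self- and partner-report, HPA activity by salivary cortisol, and PNS activity by vagal tone and regulation.

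Under Efficacy & Data Analysis, the data analysis plan first keeps that sense: "After the first wave of data collection (pretest), the cross sectional relations among the basic constructs of interest will be examined". It then names the method: "In order to understand how these markers are related to violence, t-tests will be used to understand this effect". The next sentence gives the expected direction across partners: "Each partner's HPA and PNS activity is expected to be directly linked to the violence perpetrated by their partner". For Aim 1 it gives no grouping variable, pairing or cut-off, and names no correlation or regression. It does not say whether women and men are analysed separately or as 16 people.

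Three other places matter:
- Inclusion criterion 4: "Couples must have mild to moderate forms of situational couple violence".
- Study Design: "The couples will be divided into two groups, each consisting of four couples". Allocation to immediate or delayed therapy is random.
- Screening Measures describes the CTS2 as "measuring the intensity and frequency of psychological/verbal and physical conflict", and says it is also used throughout the study.

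**The concern.** A t-test compares two means, so it needs two groups (or a pairing). To say anything about violence, the groups must differ in violence. The plan defines no such groups, and nothing in the design supplies them.

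Whoever runs the analysis must then invent a comparison. Comparing the randomised groups at pretest says nothing about violence. Splitting the CTS2 score discards information in a sample of 8 couples. A cut chosen after seeing the data also inflates the false-positive rate. The study is meant to prepare for larger ones, which need an estimate of the association with its uncertainty, and an undefined t-test does not supply that.

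**Working it through.** **1. The plan's own power figure.** The data analysis plan states power .40 at f = .80 for the t-test, with 4 couples per group and 16 participants. Alpha is not stated; I assume .05.

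| Reading | Two-sided | One-sided |
|---|---|---|
| d = 0.80, 8 v 8 partners | .32 | .45 |
| d = 0.80, 4 v 4 couples | .16 | .26 |
| d = 0.80, paired, n = 8 | .50 | .65 |
| f = .80 (d = 1.6), 4 v 4 | .48 | .64 |
| f = .80 (d = 1.6), 8 v 8 | .845 | .92 |

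None of these gives .40. A 4 v 4 comparison at one-sided alpha .10 gives .41, but the plan states no such alpha. The concern does not depend on this figure. The figure does show that the t-test was thought of in terms of the randomised groups, not groups defined by violence.

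**2. Candidate groupings in the documents.**
- Existence of IPV for the couple: constant, because criterion 4 requires it of every couple.
- Therapy v waiting group: randomised, so at pretest unrelated to violence except by chance.
- Mild v moderate violence: both words appear in criterion 4, but no rule separates them.
- Intensity: a graded CTS2 score, which yields two groups only through a cut that the plan does not define.

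**3. Cost of splitting the score.** Assumptions: n = 8 of one sex, marker and violence score bivariate normal, two-sided alpha .05. Power by simulation (400,000 runs; a separate rerun agreed within simulation error):

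| Method | r = .5 | r = .7 | r = .8 |
|---|---|---|---|
| t-test, 2 v 6 split | .13 | .22 | .29 |
| t-test, 4 v 4 median split | .15 | .29 | .41 |
| Exact Spearman | .19 | .41 | .59 |
| Pearson | .25 | .55 | .76 |

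**4. Cut chosen after seeing the data** (no true association, 300,000 runs). Taking the best of 3 v 5, 4 v 4 and 5 v 3 gives type I error .117. Taking the best of 2 v 6 through 6 v 2 gives .185.

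**5. Pooling the 16 partners as independent** (200,000 runs):

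| Split | Marker ICC .3 | .5 | .7 |
|---|---|---|---|
| Couple level | .089 | .120 | .151 |
| Individual score, partners' scores uncorrelated | .050 | .051 | .051 |
| Individual score, partners' scores correlated .5 | .061 | .070 | .079 |

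Pooling is therefore a problem only if the split is at couple level or partners' violence scores are correlated. The ICCs are assumed.

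**6. What 8 couples can show with a correlation.**
- Pearson critical value: t(.975, 6 df) = 2.447, so |r| = 2.447/√(6 + 2.447²) = .707.
- Exact Spearman null over all 8! = 40,320 orderings: |rho| = .714 gives p = .058 and .738 gives p = .046. Without ties, p < .05 needs |rho| of at least .74.
- Interval for an observed rho of .5: atanh(.5) = 0.549; SE = √((1 + .5²/2)/(8 − 3)) = √.225 = 0.474; 0.549 ± 1.96 × 0.474 = −0.380 to 1.479; back-transformed, −.36 to .90.

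**The case against.** Five points can be made for the plan.

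- **The t-test may be the t-statistic of a correlation or slope.** The plan speaks of cross-sectional relations, so this reading is possible. But it does not say so, and its power statement describes two groups. If this was meant, the wording still has to change.
- **Existence might vary between individuals.** Criterion 4 fixes it only for the couple. Whether a given partner perpetrated, or perpetrated physically, could differ within eligible couples. That stands as a possible analysis, but the plan does not specify it, words Aim 1 at couple level, and describes this violence as mutual.
- **Scores may be coarse.** The exclusions (severe items, any act repeated six or more times a year, discrepancies above 2) narrow the CTS2 range. With tied scores on assumed distributions, Spearman v median split at r = .7 is .30 v .30 (three levels at 50/30/20%), .33 v .30 (three equal levels) and .41 v .31 (six levels). At r = .5 it is .14 v .16, .15 v .15 and .20 v .15. This stands: the power gain can vanish. But there is no meaningful loss, and no cut-point has to be chosen.
- **The type I figures describe conduct the plan never proposes.** True. They show what the silence permits, not what will happen. Equally, three markers in two sexes give six p-values. If independent at .046 each, the chance of at least one false positive is 1 − .954⁶ = .25. That is why the replacement must be presented as estimation.
- **This is a feasibility study that discloses power of .40.** That limits the consequence. It does not make an undefined comparison an answer to the question.

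**Conclusion.** The concern holds. As written, the Aim 1 method cannot answer the Aim 1 question without a grouping that the plan does not define. The mismatch rests on the text alone.

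Its size rests on assumptions: normal scores, n = 8 per sex, and true correlations of .5 to .8. Under these, a median split has about 80% of the power of exact Spearman at r = .5 (.15/.19) and about 70% at r = .7 (.29/.41). With only three score levels the difference is close to nil. Type I error with a data-chosen cut is about 12–18%. No method makes 8 couples informative enough for confirmation, so the case for the change is a defined, reportable estimate more than extra power. It should be fixed before the pretest data are analysed.

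**What to change.** Replace the Aim 1 t-tests with the following.

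- At pretest, for women and men separately (n = 8 each), report the Spearman correlation between each marker (cortisol reactivity, vagal tone, vagal reactivity) and the partner's CTS2 perpetration score. Take that score as the mean of the self-report and the partner-report.
- Give each correlation a 95% confidence interval and an exact permutation p-value that allows for ties.
- State that Aim 1 concerns the intensity of violence among violent couples, and drop existence.
- Present all six correlations as estimates, not confirmatory tests.

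The text should also name the CTS2 subscale, say how cortisol reactivity is formed from the 15-, 30- and 45-minute samples, and say which assessment counts as pretest for Group 2, which is assessed before the wait and again when therapy starts.

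**Cost.** Plan wording only; the CTS2 and the markers are already collected. Aim 1 gives up its claim about existence of IPV. Spearman also has less power than Pearson if scores are close to normal (.41 v .55 at r = .7).
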